4.6 Sample Size and Power Calculation

Using historical Vaccine Confidence Index (VCI) data⁷⁰ and current vaccination rates⁷¹, a VCI threshold was determined that was significantly correlated with rates of vaccination ($p=0.0001$). Assuming the analytic approaches outlined in sections 4.7.2 and later, the sample size of 1,800

LTCWs (600 per arm) provides 80% power to detect an 8% difference in the rate of scores above this threshold between groups with a two-sided test at type I error rate of 0.05. The sample size is sufficient to retain 80% power to detect a 10% difference (assuming outcomes are randomly distributed across retained and lost subjects) after 40% attrition.

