4.8 Statistical Analysis

4.8.1 Data Source Accuracy

Initial examination of data will include descriptive statistics and frequency distributions in order to check planned analysis assumptions, identify missing data, and check data source adequacy. This process will also inform any necessary variable re-coding prior to data analysis.

4.8.2 Analyses Corresponding to Trial Aims 1 and 2

All analyses pertaining to study Aims 1 and 2 will be conducted on an intention-to-treat (ITT) basis (i.e. the arm participants were assigned to) and as-treated basis (i.e. whether they engaged with their assigned intervention or control). A detailed data analysis methodology, including planned statistical tests, timepoints for outcome assessment, and treatment of missing data, is included in Appendix B.

For Aim 1, hypothesis 1.1, we will conduct one-tailed tests (superiority analysis) to compare the impact of each of the two intervention arms against the enhanced usual practice arm on primary and secondary outcomes. For Aim 1, hypothesis 1.2, we will conduct a two-tailed test (equivalence analysis) of primary and secondary outcomes between the two intervention arms. While we hypothesize that the dialogue-based webinar intervention (Arm 1) will be superior to the social media website intervention (Arm 2), a finding of superiority, inferiority, or no distinguishable difference will be a valuable finding.

For Aim 2, hypothesis 2.1, our mediation analyses seek to identify the relationship between the interventions, mediator variables, and primary and secondary outcomes. We are interested in whether interventions operate through the mediator rather than directly affecting the outcome. If the results for Aim 1 are non-significant, we will determine whether it is a null effect of the intervention on the mediator or a null effect of the mediator on the outcome. We will determine mediation strength and mechanism generalizability by comparing effects across subgroups.

For Aim 2, hypothesis 2.2, our exploratory moderation analyses (also referred to as heterogeneity of treatment effects (HTE) analyses) seek to understand whether certain participant characteristics and beliefs influence the relationship between the interventions and vaccine confidence, as well as other secondary outcomes. We will explore moderators including (but not limited to) vaccination status, religious beliefs, age, race, ethnicity, perceived influence of others, and personal experiences with COVID-19.

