P-values ≥ 0.0001 will be reported to 4 decimal places; p-values less than 0.0001 will be reported as " <0.0001 ". The mean, standard deviation, and any other statistics other than quantiles, will be reported to one decimal place greater than the original data. Quantiles, such as median, minimum, or maximum will use the same number of decimal places as the original data. Estimated parameters, not on the same scale as raw observations (e.g. regression coefficients) will be reported to 3 significant figures.

Adherence to interventions

Analysis of both intention-to-treat (ITT) and as-treated populations will be performed. All participants who are randomized to a trial arm will be included in the ITT analyses. Participants who adhere to major engagement criteria for their primary intervention will be included in the as-treated analyses.

Analysis methodology

Aim 1

To compare the impact of two interventions delivered online: 1) a dialogue-based webinar (webinar) using the existing COVID-19 Option Grid conversation aid and, 2) an interactive and, dynamic, and multi-component social media web application (social media website), compared to enhanced usual practice (link to Centers for Disease Control (CDC) vaccine website), on COVID-19 vaccine confidence (primary outcome), and other secondary outcomes among LTCWs. We hypothesize that each intervention will be superior to enhanced usual practice at increasing vaccine confidence (*Hypothesis 1.1*) and that the dialogue-based webinar intervention will be superior to the social media arm at increasing vaccine confidence (*Hypothesis 1.2*).

Corresponding analyses

Primary outcome

The primary outcome is the binary classifier of vaccine confidence derived from the three-item Vaccine Confidence Index (VCI), evaluated at 3 weeks post-randomization, which will be analyzed by randomization arm. The determined binary predictors of intervention outcomes will be compared using two-proportion z-tests to identify significant differences between each intervention and enhanced usual practice (Arm 1 vs Arm 3 & Arm 2 vs Arm 3 - superiority analyses) and between the intervention arms (Arm 1 vs Arm 2 - two-tailed equivalency analysis).

Secondary outcomes

- *Change from baseline in COVID-19 Vaccine Confidence.* Analysis of change from

baseline will be based on a binary classifier whether the average score increases (1) or does not increase (2) at T1, T2, and T3 versus baseline.

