The primary outcome involves three separate tests, one a two-tailed equivalence test and two one-tailed superiority tests. In order to achieve a family-wise error rate less than 0.050, the Bonferroni method was employed to set a p-value threshold at 0.016 for each of the three primary outcome analyses. For each comparison, mean-value separation will be considered significant based on a 98.4% confidence interval, which translates to +/- 2.45 times the standard

error for the sample mean for the equivalence test and greater than 2.15 times the standard error for the superiority analyses.

Based on the high number of secondary outcome analyses (cross-sectional T1; change from baseline; ITT; as-treated), results data for these outcomes will be viewed in more aggregate form as trending in one direction or not, rather than adopting a specific Bonferroni-corrected p-value threshold.

References

1. B. Rocks, Interval Estimation for the “Net Promoter Score.” *Am. Stat.* 70, 365–372 (2016).
2. R. M. Baron, D. A. Kenny, The moderator–mediator variable distinction in social psychological research: Conceptual, strategic, and statistical considerations. *J. Pers. Soc. Psychol.* 51, 1173–1182 (1986).
3. T.E. Raghunathan, J.M. Lepkowski, J. Van Hoewyk, P. Solenberger, et al. A multivariate technique for multiply imputing missing values using a sequence of regression models. *Surv. Methodol.* 27, 85–96 (2001).

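### The webinar versus social media primary comparison is called an equivalence test but is a two-sided test of difference with no margin, and its ±2.45 SE rule does not match the stated 0.016 threshold and 98.4% interval

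*Combined protocol and SAP*

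**What the plan says.** Appendix B (Aim 1, primary outcome) compares the binary confidence classification at three weeks using two-proportion z-tests intended to find significant differences. The tests are run for each intervention against enhanced usual practice and "between the intervention arms (Arm 1 vs Arm 2 - two-tailed equivalency analysis").

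Section 4.8.2 uses the same label: "we will conduct a two-tailed test (equivalence analysis) of primary and secondary outcomes between the two intervention arms". It then says that "a finding of superiority, inferiority, or no distinguishable difference will be a valuable finding". Hypothesis 1.2 itself is directional: the webinar is expected to be superior to the social media website.

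The Multiple testing section of Appendix B describes the primary family as "one a two-tailed equivalence test and two one-tailed superiority tests" and uses Bonferroni to "set a p-value threshold at 0.016 for each of the three primary outcome analyses". It calls a separation of means significant on the basis of a "98.4% confidence interval, which translates to +/- 2.45 times the standard" error for the equivalence test, and more than 2.15 standard errors for the superiority tests.

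Section 4.6 gives the only reference differences. The sample of 600 per arm "provides 80% power to detect an 8% difference in the rate of scores above this threshold between groups", and it is said to "retain 80% power to detect a 10% difference (assuming outcomes are randomly distributed across retained and lost subjects) after 40% attrition".

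**The concern.** An equivalence test needs a margin. Equivalence is concluded when the confidence interval lies wholly inside it. A two-proportion z-test with a critical value works the other way round: it rejects equality when the estimate is far enough from zero, and a failure to reject says nothing about how close the arms are. The plan attaches the first name to the second procedure, in both the protocol body and the SAP, for one of its three primary comparisons. Section 4.8.2 extends the label to the secondary outcomes. A reader of the results could take a non-significant webinar versus website contrast as evidence that the two are equivalent.

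The Multiple testing section also states its decision threshold in three forms: a p-value, a confidence level and a multiple of the standard error. These should be the same rule. If they are not, a result can be significant under one and not under another.

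**Working it through.** **Label against method.** Set side by side, only the label points to equivalence.

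| Element | Place | Points to |
|---|---|---|
| Label | 4.8.2; Appendix B, Aim 1 and Multiple testing | Equivalence |
| Hypothesis 1.2 | 3.2; Appendix B, Aim 1 | Superiority |
| Test (two-proportion z-test for differences) | Appendix B, Aim 1 | Difference |
| Decision rule (separation beyond a multiple of the SE) | Appendix B, Multiple testing | Difference |
| Permitted readings | 4.8.2 | Difference (equivalence not listed) |
| Power statement | 4.6 | Difference |
| Margin, two one-sided tests, or interval-within-margin rule | Nowhere | – |

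**Threshold.** Inputs from Multiple testing: 0.016 per test, 98.4% interval, ±2.45 SE (two-tailed), 2.15 SE (one-tailed).

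- One-tailed: z(1 − 0.016) = 2.144, and 2.15 SE is a one-sided p of 0.0158. The stated figure reproduces after rounding up.
- Two-tailed: z(1 − 0.016/2) = 2.409. The stated 2.45 does not reproduce. 2 × [1 − Φ(2.45)] = 0.0143, which is a 98.57% interval.
- Alternatives: unrounded Bonferroni (0.05/3 = 0.0167) gives 2.394; Šidák gives 2.388; t quantiles give 2.412 (1,198 df, 600 per arm) and 2.415 (718 df, 360 per arm). None gives 2.45.
- Family-wise error: 3 × 0.016 = 0.048 under the p rule; 0.0143 + 2 × 0.0158 = 0.0459 with these rounded values (0.0458 unrounded) under the SE rules. Both are below 0.050.
- Power cost of 2.45 instead of 2.409 (rates centred on the mid-rate shown; unpooled SE):

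| Difference | n per arm | Mid-rate 30% | Mid-rate 50% |
|---|---|---|---|
| 8 points | 600 | 73.4% → 72.1% | 64.5% → 62.9% |
| 8 points | 360 | 47.7% → 46.1% | 39.9% → 38.3% |
| 10 points | 600 | 91.8% → 91.2% | 85.8% → 84.9% |
| 10 points | 360 | 70.4% → 69.0% | 61.3% → 59.8% |

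The loss is 0.6 to 1.6 points.

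**What a null result could exclude.** The documents give no base rate, so a common rate p in both arms is assumed. Eight points, the target in 4.6, is used as a yardstick; the plan does not call it a margin.

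- Half-width of the 98.4% interval = 2.409 × √[2p(1 − p)/n]. For p = 0.5, n = 600: 2.409 × 0.02887 = 6.95 points.
- Eight points is excluded only if the observed difference is smaller in size than 8 minus the half-width. For that case: 8 − 6.95 = 1.05 points.
- With a true difference of zero, the share of non-significant results that do not exclude 8 points is 1 − [2Φ(x/SE) − 1]/0.984, where x is that limit.

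| n per arm | Rate | Half-width | Limit x | Share not excluding 8 points |
|---|---|---|---|---|
| 600 | 20% or 80% | 5.56 | 2.44 | 28% |
| 600 | 30% or 70% | 6.37 | 1.63 | 53% |
| 600 | 50% | 6.95 | 1.05 | 71% |
| 360 | 20% or 80% | 7.18 | 0.82 | 78% |
| 360 | 30% or 70% | 8.23 | none | 100% |
| 360 | 50% | 8.98 | none | 100% |

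The 360 rows are the 40% attrition case in 4.6 (600 × 0.6).

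**The case against.** The strongest reply is that the intent is already clear. Section 4.8.2 lists the possible findings, and equivalence is not among them; the hypothesis is superiority; no passage plans a claim of equivalence. On this view only a wrong word remains. The point about intent stands, and it is why relabelling is enough. It does not make the label harmless: the word recurs in three places covering a primary comparison, and nothing rules out the reading it invites.

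On the threshold, the p-value and the interval agree exactly, and 2.45 looks like a slip in a derived figure. The error is conservative, and under the null the test statistic falls between the two cut-offs with probability 0.016 − 0.0143 = 0.0017. This also stands: the numerical point is minor beside the label.

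The precision figures depend on assumed rates. At 20% the share at 600 per arm falls to 28%, and section 4.3.1 aims to enrol people with low confidence, so low rates are plausible. A formal equivalence test at one-sided 0.016 would use 2.144 rather than 2.409 standard errors. With an assumed 8-point margin, no true difference and 600 per arm, it would succeed 47% of the time at a 50% rate and 62% at 30%; at 360 per arm, 0.2% and 16%. The figures therefore show that a null result often would not exclude 8 points. They are not the power of an equivalence design, which the plan does not specify.

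**Conclusion.** The concern holds. The webinar versus social media comparison is a two-sided test of difference under an equivalence label, and without a margin it cannot yield a conclusion of equivalence. That follows from the text and needs no assumption. How often a null result would leave 8 points open does depend on assumptions: a common confidence rate of 30% to 70%, no true difference, and the 98.4% interval. The answer is then 53% to 71% at 600 per arm and always at 360; at a 20% or 80% rate it is 28% and 78%.

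The ±2.45 multiplier is wrong for the stated 0.016 and 98.4%; the value is 2.41. A two-sided p between 0.0143 and 0.016 is significant by the p-value rule and not by the standard-error rule. Family-wise error stays below 0.050 either way. Both points should be corrected, and the label matters more.

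**What to change.** - In section 4.8.2 and in Appendix B (Aim 1 primary outcome, and Multiple testing), replace the equivalence and equivalency labels with a two-sided test of difference.
- Make the three expressions of the threshold agree: 2.41 standard errors if 0.016 and 98.4% are kept, or 2.39 with p < 0.0167 and a 98.33% interval if the exact Bonferroni value 0.05/3 is used.
- Report the Arm 1 minus Arm 2 difference with that interval, and state that a non-significant result will be reported as no distinguishable difference and not as equivalence.
- If a conclusion of equivalence is wanted, pre-specify a margin with its justification, an interval-within-margin rule, and the power for it.

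The first three changes cost wording and one number (with the p threshold and interval restated if 0.05/3 is chosen). Design, sample size, data collection and the planned z-test are unchanged. The last is needed only if equivalence becomes an aim, and the sample size would then have to be checked against the chosen margin.

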4.5.2 Secondary Outcomes and Other Data

Change from baseline in COVID-19 Vaccine Confidence. Additional analysis of the VCI data will include the proportion of positive VCI responses at subsequent evaluations and the individual change in VCI between baseline and each follow-up evaluation. Subdomains of the VCI will be evaluated separately from the composite score.

Likelihood of recommending (promoting) COVID-19 vaccination. Adapted Net Promoter Score (NPS) questions⁵⁰ will assess the likelihood that participants would recommend 1) COVID-19 vaccination to others who are unvaccinated, and 2) COVID-19 booster vaccination to a coworker. Similar questions have been recommended previously^{51,52}. We will adopt the traditional scoring approach that categorizes respondents as promoters, passives, or detractors.

COVID-19 vaccine uptake and intent. We will assess uptake of the COVID-19 vaccines (any dose, initial series completion, and booster completion) using four questions that we developed. For those who report not being vaccinated or boosted, intent to get a COVID-19 vaccine (initial series or booster) will be assessed using two questions broadly adapted from prior work⁵³. All participants will also be asked if they would get regular vaccines in the future if they are recommended, using a single question.

Feeling informed about the COVID-19 vaccines. We will assess the degree to which participants' feel informed about the COVID-19 vaccines (have enough information and understand that information), using two self-developed questions. Our operational definition of feeling informed was influenced by the Decision Self-Efficacy Scale⁵⁴.

Identification of COVID-19 vaccine information and misinformation. We will assess participants' identification of COVID-19 vaccine-related information and misinformation, using four questions that were shown to have low rates of correct identification in the pre-launch survey data (see 4.1.2). Some questions were self-developed and some were adapted from prior work⁴³.

Trust in COVID-19 information from different sources. We will assess participants' trust in COVID-19 information provided by different people and organizations, using three items broadly adapted from prior work⁵⁵.

Change from baseline in secondary outcomes. Additional analysis of secondary outcomes will include their assessment at subsequent evaluations and the individual change in secondary outcomes between baseline and each follow-up evaluation.

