Appendix A

COVID-19 Vaccine Option Grid™

Note: This version of the Option Grid is dated May 2022 and has had multiple updates to content since this date. The current version is available at <https://decisions.dynamed.com/tools/vaccine-options-for-covid-19>

EBSCO Clinical Decisions

optiongrid  Page 1 of 3

COVID-19 Vaccine Options

This decision aid is for people or caregivers of people 5 years or older. Only the Pfizer/BioNTech vaccine is available for people less than 18 years old. People with serious

allergic reactions in the past should talk with their healthcare professional before getting the vaccine. This information is for vaccines available in the United States.

QUESTIONS	No Vaccine	Pfizer/BioNTech and Moderna Vaccines	Johnson & Johnson/Janssen Vaccine
What does the option involve?	Continue to distance, avoid gatherings, wear a mask, and clean your hands often.	You will get a total of 2 shots in your arm, 3 to 8 weeks apart . Some countries use different times for the shots.	You will get 1 shot in your arm .
What are the benefits?	You will not have the side effects that are common with the COVID-19 vaccine.	The vaccine helps lower your risk of getting COVID-19. You will also be much less likely to get seriously ill if you get COVID-19. 2 weeks after the second shot , it is safer to do things you did before the pandemic . You should still follow rules and guidance about wearing a mask and distancing. People being fully vaccinated helps keep COVID-19 under control .	The vaccine helps lower your risk of getting COVID-19. You will also be much less likely to get seriously ill if you get COVID-19. 2 weeks after the shot , it is safer to do things you did before the pandemic . You should still follow rules and guidance about wearing a mask and distancing. People being fully vaccinated helps keep COVID-19 under control .

COVID-19 Vaccine Options (Continued)

QUESTIONS	No Vaccine	Pfizer/BioNTech and Moderna Vaccines	Johnson & Johnson/Janssen Vaccine

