- *Likelihood of recommending COVID-19 vaccination (others not vaccinated)*. This question will be evaluated using a Net Promoter Score (NPS) approach, adding one for each positive response, zero for neutral, and subtracting one for each negative response, then dividing by the number of non-missing responses for each trial arm. NPS values will be compared using Wald intervals [1].
- *Likelihood of recommending COVID-19 booster vaccination (coworker)*. This question will be evaluated using the NPS approach, described above.
- *COVID-19 vaccine uptake (any dose)*. This will be evaluated as a binary classifier compared across trial arms using two-proportion z-tests.
- *COVID-19 vaccine uptake (initial series completion)*. For participants who have received any dose of a COVID-19 vaccine, this will be evaluated as a binary classifier compared across trial arms using two-proportion z-tests.
- *COVID-19 vaccine uptake (booster completion)*. For participants who have completed their initial vaccine series, this will be evaluated as a three category variable (No, Not sure, Yes) compared across trial arms using chi-squared tests.
- *COVID-19 vaccine intent (initial series)*. For participants who are unvaccinated, we will assess their intentions of getting a COVID-19 vaccine, this will be evaluated using the Net Promoter Score approach, where the three responses – Yes, Not Sure, No – will be evaluated as analogous to promoter, neutral, and detractor, respectively. The question will be evaluated using the NPS analysis, described above.
- *COVID-19 vaccine intent (booster)*. For participants who have completed an initial vaccine series, this will be evaluated using the Net Promoter Score approach, where the three responses – Yes, Not Sure, No – will be evaluated as analogous to promoter, neutral, and detractor, respectively. The question will be evaluated using the NPS analysis, described above.
- *COVID-19 vaccine intent (future vaccine recommendations)*. Participants' intent to get COVID-19 vaccines regularly in the future if they are recommended will be evaluated using the Net Promoter Score approach, where the three responses – Yes, Not Sure, No – will be evaluated as analogous to promoter, neutral, and detractor, respectively. The question will be evaluated using the NPS analysis, described above.

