- *Feeling informed about the COVID-19 vaccines*. The degree to which participants' feel informed about the COVID-19 vaccines (have enough information and understand that information) will be evaluated using a continuous variable, calculated as the mean scale

score across two items ((1) having enough information, (2) understanding the information) for each participant. The mean of all mean scores will be compared across trial arms with two-sample unpaired t-tests.

- *Identification of COVID-19 vaccine information and misinformation.* Subjects' identification of COVID-19 vaccine information and misinformation will be scored on a scale of zero to four and treated as a continuous linear variable. Results will be compared across trial arms with two sample unpaired t-tests.
- *Trust in COVID-19 information from different sources.* Subjects' trust in COVID-19 information from different sources will be evaluated using a continuous variable, calculated as the mean scale score across three items for each participant. The mean of all mean scores will be compared across trial arms with two-sample unpaired t-tests.
- *Change from baseline in secondary outcomes.* Change from baseline will be scored as a binary variable with an increased value scored as one and a no change or decreased value scored as zero. For each evaluation after baseline, each arm will be compared using two-proportion z-tests. For vaccine and booster intent questions, where the intent question is not repeated if the participant indicates an increase in vaccination status, intent will be imputed from uptake. To be clear, an individual who is unvaccinated at T0, then returns at T1 and indicates that he or she is now vaccinated, will be presented with the vaccine intent question at T0 but not at T1. Because the individual is now vaccinated, asking about vaccine intent at T1 would be confusing. For analyzing change in vaccine intent, the individual whose vaccine status increases would be considered to have positive intent at T1. A similar approach will be used for booster intent.
- *As treated analysis of primary and secondary outcomes.* Primary and secondary outcome analyses will be repeated, limited to the as treated samples.

Aim 2

To determine if LTCWs' characteristics and other factors mediate and moderate the interventions' impact on vaccine confidence and other secondary outcomes.

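### Four T1 secondary outcomes (series completion, booster completion, initial-series intent, booster intent) are compared in groups set by vaccination status after randomization, so these contrasts are not protected by randomization

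*Combined protocol and SAP*

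**What the plan says.** Table 1 of Appendix B places all four outcomes at T1, which section 4.7.5 sets at three weeks after baseline and randomization. The Secondary outcomes list in Appendix B then defines who is compared:

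- Series completion: "For participants who have received any dose of a COVID-19 vaccine, this will be evaluated as a binary classifier compared across trial arms".
- Initial-series intent: "For participants who are unvaccinated, we will assess their intentions of getting a COVID-19 vaccine".
- Booster intent: "For participants who have completed an initial vaccine series, this will be evaluated using the Net Promoter Score approach".
- Booster completion: also limited to those who have completed the initial series, as a three-category variable with a chi-squared test.

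Section 4.5.2 describes who is asked about intent: "For those who report not being vaccinated or boosted, intent to get a COVID-19 vaccine (initial series or booster) will be assessed". The change-from-baseline item in Appendix B adds that "the intent question is not repeated if the participant indicates an increase in vaccination status", and supplies a scoring rule: "For analyzing change in vaccine intent, the individual whose vaccine status increases would be considered to have positive intent at T1". It says booster intent will be handled similarly. For secondary outcomes in general, "Change from baseline will be scored as a binary variable with an increased value scored as one".

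Any-dose uptake has no status restriction. Under Multiple testing, secondary outcomes have no p-value threshold and are read in aggregate by the direction in which they trend.

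**The concern.** Getting vaccinated is something the interventions try to bring about, and any-dose uptake is itself a secondary outcome. If status at T1 decides who is in a T1 comparison, the arms being compared are no longer the randomized groups.

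- **Series completion.** A new first-dose taker enters the denominator, usually as a non-completer. The arm that persuaded more people to start can then show a lower completion rate with the same number of completers.
- **Initial-series intent.** A newly vaccinated person, likely among the most favorable, leaves the group. The positive-intent rule would restore that person, but it is written only for change from baseline.
- **Booster outcomes.** People who complete the series after T0 enter both groups. Newly boosted people are no longer asked about booster intent and leave that group.

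Because secondary results are read by direction, even a modest distortion can affect the summary.

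**Working it through.** The documents state no figure for these outcomes, so there is none to reproduce. They also give neither the baseline vaccination mix nor uptake by three weeks. Every count below is an assumption, apart from 600 per arm and 40% attrition (section 4.6).

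**1. Series completion.** The planned rate is completers at T1 divided by people with any dose at T1. It falls whenever new starters are less complete at T1 than people already dosed at T0. Appendix A, in its May 2022 version (since updated), gives "2 shots in your arm, 3 to 8 weeks apart" for the two-shot vaccines. A two-shot series begun after T0 is therefore rarely complete at three weeks; a one-shot series could be.

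Take equal completers in both arms and no new starter complete by T1 (two-proportion z-test):

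| Assumed unvaccinated at T0 | New starters | Planned rates | Difference (points) | z |
|---|---|---|---|---|
| 100/600 (17%) | 3 vs 2 | 480/503 vs 480/502 | -0.19 | -0.15 |
| 100/600 | 5 vs 2 | 480/505 vs 480/502 | -0.57 | -0.43 |
| 100/600 | 10 vs 2 | 480/510 vs 480/502 | -1.50 | -1.08 |
| 100/600 | 20 vs 2 | 480/520 vs 480/502 | -3.31 | -2.22 |
| 60/600 (10%) | 3 vs 1 | 520/543 vs 520/541 | -0.35 | -0.30 |
| 30/600 (5%) | 2 vs 1 | 555/572 vs 555/571 | -0.17 | -0.17 |

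After 40% attrition the 20 vs 2 case is 288/312 vs 288/301, z = -1.75.

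A real gain can also be hidden. Let 500 per arm be dosed at T0, of whom 480 are complete and 20 partly vaccinated. Let 5 vs 2 of the partly vaccinated finish and 5 vs 2 new people start:

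- Planned: 485/505 vs 482/502 = +0.02 points.
- Among those not series-complete at T0 (100 + 20 = 120): 5/120 vs 2/120 = 4.2% vs 1.7%, or +2.5 points (z = 1.15).

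**2. Initial-series intent.** Let k be the share of the T0-unvaccinated who are vaccinated by T1, and NPS_all the score with them counted as positive. The score among those still asked is

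NPS_remaining = (NPS_all - k)/(1 - k),

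which is lower than NPS_all by k(1 - NPS_all)/(1 - k) whenever k > 0 and NPS_all < 1. At equal NPS_all, the arm with more newly vaccinated people looks worse: with k = 10% vs 5% and NPS_all = -0.2 in both arms, the difference is -0.07 instead of 0.

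Now take 100 unvaccinated per arm at T0, answering Yes/Not sure/No 30/30/40. Five people convert to Yes in the active arm, and all who get vaccinated come from Yes. Control, with 2 vaccinated, scores (28 - 40)/98 = -12.24 (in points, NPS × 100).

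| Vaccinated, active vs control | Converts from Not sure (difference under the rule +5) | Converts from No (difference under the rule +10) |
|---|---|---|
| 5 vs 2 | (30-40)/95: +1.7 | (30-35)/95: +7.0 |
| 7 vs 2 | (28-40)/93: -0.7 | (28-35)/93: +4.7 |
| 10 vs 2 | (25-40)/90: -4.4 | (25-35)/90: +1.1 |

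The shrinkage appears in both columns. The sign change appears in only one.

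**3. Booster intent.** The same formula covers people who leave. With k = 5-20%, a control score of -0.10, nobody newly boosted in the control arm and no entrants, the difference is -0.06 to -0.28 where the true difference is 0. Adding new series completers of up to 5% of the group, with any intent, widens this to between 0.00 and -0.31.

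**4. Booster completion.** The denominator again depends on status after T0, because new series completers join it. No size was calculated.

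**The case against.** The strongest reply is that the plan already covers much of this. It foresaw the intent problem and has a change-from-baseline analysis that counts the newly vaccinated as positive. Any-dose uptake counts new starters directly. Change-from-baseline completion gives partial protection if people unvaccinated at T0 are kept in as not complete; that is a natural reading under intention to treat, but it is not stated. Secondary results are also read in aggregate, so one contrary rate would not stand alone. All this limits the consequences, but it does not make the four T1 contrasts randomized comparisons.

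Completion among the dosed can also be defended as one step of an uptake cascade. It is a true description of that rate, but not an effect of the arm.

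Three stronger readings should be resisted:

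- *Intent reverses once a given number are vaccinated.* Any such threshold depends on the assumed response mix and on where converts come from, as the two columns above show.
- *Section 4.5.2 and Appendix B contradict each other on booster intent.* One says who is asked, the other names a group and divides by non-missing responses, so they can be read together. The wording is loose and should be aligned.
- *Booster outcomes are biased against the active arms.* People enter as well as leave, so the net direction is open.

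Finally, the repair changes what is estimated: completion becomes conversion among those not complete at T0, in a smaller group (120 rather than about 500 per arm in the example). That cost is real.

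**Conclusion.** The point holds for these four T1 secondary outcomes. It rests on reading the restrictions as status at T1. For intent, the change-from-baseline text confirms this; for completion, nothing fixes status at T0.

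The direction is a tendency for series completion and initial-series intent. It would not hold for completion if new starters mostly used a one-shot series, or if an arm mainly led partly vaccinated people to finish. An intent difference can even be overstated: with k = 10% vs 8% and NPS_all of +0.4 vs -0.2, it is 0.64 instead of 0.60.

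The size is unknown and probably small if few people change status by T1; section 4.4.2 reports low webinar exposure early in data collection. In the 600-per-arm completion table, only 20 vs 2 new starters reaches nominal significance, and it does not after 40% attrition.

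A reader might infer that the trial's main conclusion is at risk. The documents do not support that: the primary outcome, any-dose uptake, future-vaccine intent and change-from-baseline intent are unaffected. The change is still worth making, because the mechanism follows from the text and the repair is cheap.

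**What to change.** Keep T1 as the time point and amend the Secondary outcomes text in Appendix B:

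1. Define denominators by T0 status: not series-complete at T0 for series completion; unvaccinated at T0 for initial-series intent; series-complete and unboosted at T0 for booster intent and booster completion. State where a T0 'Not sure' booster answer falls.
2. Apply the existing rule, that a status increase counts as positive intent, to the T1 cross-sectional intent comparisons.
3. Align section 4.5.2 and Appendix B on who is in the booster-intent group.
4. State that people unvaccinated at T0 count as not complete in change-from-baseline completion.
5. Keep the any-dose-conditional completion rate as descriptive only, if wanted, and note in the report that a two-shot series begun after randomization will rarely be complete at T1.

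Apply this within the existing requirement for T0 and T1 primary outcome data and the planned imputation, and use the same denominators for any T2 or T3 assessment.

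**Cost:** a few lines of text and no new data, since baseline vaccination status is collected at T0 and uptake and intent are already surveyed. The groups are smaller and the estimates less precise, and T1 intent becomes a combined intent-or-uptake measure, which should be labeled as such.
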